## **PROPHYLACTIC MEASURES**

Subjects should receive allopurinol or rasburicase and other treatment considered appropriate for tumor lysis prophylaxis in cycle 1 as deemed necessary by the treating physician.

Subjects should receive prophylactic anti-emetics prior to romidepsin administration.

G-CSF may be given at each cycle. (Neulasta should only be given if there is a 14 day interval to the next dose).

As noted previously, Serum potassium ( $K^+$ ) and Serum Magnesium ( $Mg^+$ ) will be verified before each dose of Romidepsin. Values  $\leq$  laboratory LLN will be corrected prior to Romidepsin administration.

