#### **2.4.2 Phase I Experience and Determination of MTD**

Twenty-six patients were enrolled in the Phase I study and were evaluable for toxicity. Median age was 51 yrs (23-79) and 58% were male. The median number of prior therapies was 6.5 (range 1-18). Histologies included HL (N=12), DLBCL (N=5), follicular lymphoma (N=3), ATLL (N=2), CTCL (N=2), cutaneous ALCL (N=1), T-ALL (N=1). The entry dose in cohort 1 was azacytidine at 100 mg day 1 to 14 with romidepsin 10 mg/m^2 day 8, 15 every 21 days with no DLT detected. There were 2 DLTs in cohort 2 (azacytidine 200mg day 1 to 14 with romidepsin 10 mg/m^2 day 8, 15 every 21 days) consisting of 1 Grade 3 thrombocytopenia and 1 Grade 3 pleural effusion. In cohort 3, 3 additional patients were evaluated using the every 28 days schedule at the same dose level and no thrombocytopenia and/or other DLTs were observed. Dose escalation was continued until 2 DLT were observed in cohort 7 (azacytidine 300mg day 1 to 21 with romidepsin 14mg/m^2 day 8, 15, 22 every 35 days which resulted in 1 Grade 4 thrombocytopenia and 1 Grade 4 neutropenia. This dose level was declared maximum administered dose (MAD). Patients dosed at the maximum tolerated dose (MTD) of azacytidine 300 mg day 1 to 14 and romidepsin 14 mg/m^2 day 8, 15, 22 every 35 days did not experience any toxicities.

The toxicities reported in >10% of patients included: grade 3/4 toxicities represented by febrile neutropenia (19.2%) and thrombocytopenia (19.2%); grade 2 toxicities represented by back pain (7.7%), fatigue (11.5%), nausea (34.6%), vomiting (19.2%), pain (7.7%) and peripheral sensory neuropathy (7.7%) and grade 1 toxicities including fatigue (38.5%), nausea (23%), diarrhea (19.2%), malaise (19.2%), vomiting (19.2%), anorexia (15.4%), pain (15.4%), constipation (11.5%), cough (11.5%), fever (11.5%), general disorders and administration site complains (11.5%), dyspnea (7.7%), hypokalemia (7.7%), insomnia (7.7%), oral mucositis (7.7%) and pruritus (7.7%).

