#### 5.1.6 Dose De-escalation Decision Rules:

If a DLT is reached in the first cycle for a given patient, then the previous dose level will be utilized for that particular patient in subsequent cycles. Should that patient experience a second DLT at that lower dose, they will be removed from the study. Dose-escalation will resume until the maximally administered dose is achieved or MTD is reached.

For example, according to the schema in Table 2, if DLT is reached at dose level 1 (romidepsin 10 mg/m^2 and oral 5-azacitidine 100 mg/m^2), the frequency of romidepsin will be reduced to a Day 8 only dose. Dose escalation can resume starting at that point according to dose escalation rules (Table 3). The same

applies if DLT is reached at all other levels prior to dose level four.

Toxicities in cycles 2 and following may be accommodated by treating patients at one dose level below the present cohort. Toxicity in cycles 2 and beyond will not affect dose escalation for future patients.

In the Phase 2, de-escalation should follow the Phase 1 escalation guidelines. For instance, any recurrent Grade 3 toxicity, up to 3 de-escalations will be allowed, with the doses of the drugs being reduced to that described in Cohort 5 (azacytidine 300 mg Day 1-14, and romidepsin 14 mg/m^2 Day 8 and 15 every 28 days) → Cohort 4 (azacytidine 300 mg Day 1-14, and romidepsin 10 mg/m^2 Day 8 and 15 every 28 days) and then Cohort 3 (azacytidine 200 mg Day 1-14, and romidepsin 10 mg/m^2 Day 8 and 15 every 28 days). Any patient experiencing a Grade 4 toxicity should just be immediately dose reduced according to the guideline above. In addition, patients can be dose reduced per the treating physicians discretion.

Specifically, for hematologic toxicities, patients may receive GCSF for neutropenia. For cases where patients miss a dose secondary to a recurrent Grade 3 ANC or platelet count, or Grade 4 hematologic toxicity, dose reductions should occur as noted above at the physicians discretion (i.e. reduce to Cohort 5, then 4 then 3).

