### **5.1.7 Prophylactic Medicines and Supportive Care**

Romidepsin is moderately emetogenic. Standard institutional guidelines for anti-emetics will be used. Supportive treatment may include additional anti-emetics, anti-diarrheal, anti-pyretics, anti-histamines, analgesics, antibiotics, and blood products. Patients who experience indigestion or gastroesophageal reflux symptoms on Romidepsin may be treated with Proton Pump Inhibitors (PPIs) as well as H2 blockers as clinically indicated.

Patients who have pre-existing chronic anemia prior to receiving oral 5-azacitidine and romidepsin may continue to receive erythropoietin or darbepoietin. Post cycle 1, colony stimulating growth factors (e.g., filgrastim, peg-filgrastim, and sargramostim) may be used in patients who experience hematological toxicity per American Society of Clinical Oncology (ASCO) guidelines. After initiating treatment, anemia may be managed with growth factors according to the ASCO guidelines: 2006 Update of Recommendations for the Use of White Blood Cell Growth Factors: An Evidence-Based Clinical Practice Guideline <http://www.jco.org/cgi/content/full/24/19/3187>. Neulasta should only be used if the interval to the next dose is ≥14 days.

Patients will be permitted to receive appropriate supportive care measures as deemed necessary by the treating physician including but not limited to the items outlined below:

- **Diarrhea:** Diarrhea should be treated promptly with appropriate supportive care, including loperamide. Loperamide should not be taken prophylactically. Patients should be instructed to begin taking loperamide at the first sign of: 1) poorly formed or loose stool, 2) occurrence of more bowel movements than usual in one day or 3) unusually high volume of stool. Loperamide should be taken in the following manner: 4 mg at first onset of diarrhea, then 2 mg after each unformed stool. The daily dose of loperamide should not exceed 16 mg/day. Loperamide should be deferred if blood or mucus is present in the stool or if diarrhea is accompanied by fever. In this setting, appropriate diagnostic microbiologic specimens should be obtained to exclude an infectious etiology. Patients should also be advised to drink liberal quantities of clear fluids.

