- **Nausea/vomiting:** Romidepsin is moderately emetogenic. Ondansteron 8 mg IV will be given prior to Romidepsin injections. Nausea and vomiting should be treated aggressively, with agents such as prochlorperazine, metoclopramide, 5-HT-3 inhibitors, or benzodiazepines. Patients should be strongly encouraged to maintain liberal oral fluid intake during therapy, especially during the initial 14 days of each treatment cycle.
- **Fatigue:** May be cumulative with increasing cycles of therapy. Can be treated as indicated by the treating physician.
- **Anemia:** Treatment with oral 5-azacitidine and romidepsin can cause dose-related anemia. Transfusions or erythropoietin may be utilized as clinically indicated for the treatment of anemia, but should be clearly noted as concurrent medications.
- **Thrombocytopenia:** Treatment with Oral 5-azacitidine and Romidepsin can cause dose-related thrombocytopenia. Transfusion of platelets may be used if clinically indicated. Dose modification for thrombocytopenia is allowed in a manner consistent with the guidelines for dose modification (Section [6.3]). Prophylactic folic acid and vitamin B12 supplements may be necessary to reduce hematologic toxicity.
- **Neutropenia:** Prophylactic use of colony-stimulating factors including G-CSF, pegylated G-CSF or GM-CSF should not be utilized during the first cycle of therapy. These factors may be utilized if clinically indicated in subsequent cycles.
- **Hypokalemia or hypomagnesemia** should be corrected prior to administration of Romidepsin, and consideration should be given to monitoring potassium and magnesium in symptomatic patients (e.g. patients with nausea, vomiting, diarrhea, fluid imbalance or cardiac symptoms.)
- **Oral Mucositis:** Oral 5-azacitidine may cause mucositis (includes stomatitis or mucosal inflammation of gastrointestinal and genitourinary tracts); which may require dosage modification. Prophylactic folic acid and vitamin B12 supplements are necessary to reduce treatment-related mucositis.
- **Hepatotoxicity:** Liver function test abnormalities have been observed with Oral 5-azacitidine use. Persistent abnormalities may indicate hepatotoxicity and may require dosage modification.

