## **5.2 Dose-Limiting Toxicity**

A dose limiting toxicity (DLT) is defined as any toxicity not specifically included in section 5.2 that occurs within cycle 1 and is considered at least "possibly related to study drug administration." DLT is also defined as any toxicity possibly related to drug, occurring up to 7 days after completion of cycle 1 that results in a delay of initiating cycle 2. For patients who discontinue study drug administration after Cycle 1, DLT will be defined as any toxicity not specifically included in section 5.2 that occurs within 30 days of the last dose of drug on study, in cycle 1 that is considered at least possibly related to study

drug.

DLTs include:

- Hematologic dose-limiting toxicity will be defined as either Grade 4 neutropenia that does not resolve to  $\leq$  Grade 2 within  $\leq$  7 days, any Grade 4 thrombocytopenia, or any Grade 5 hematologic toxicity. At least three patients in each cohort must be evaluable for hematologic toxicity.
- Non-hematologic dose-limiting toxicity will be defined as any Grade 3, 4 or 5 non-hematologic toxicity, with the specific exception of:
- Grade 3 nausea or Grade 3 vomiting that in the opinion of the investigator occurs in the setting of inadequate compliance with supportive care measures specified in Section 5.1.7 and lasts for less than 48 hours.
- Grade 3 diarrhea that in the opinion of the Investigator occurs in the setting of inadequate compliance with supportive care measures specified in Section 5.1.7 and lasts for less than 48 hours.
- Grade 3 dehydration that, in the opinion of the investigator, occurs in the setting of inadequate compliance with supportive care measures specified in Section 5.1.7 and lasts for less than 48 hours.
- Grade 3 acidosis or alkalosis that responds to medical intervention by returning to  $\leq$  Grade 2 within 48 hours.
- Isolated (i.e. no other abnormalities) Grade 3 elevation of liver function tests (LFTs) without associated clinical symptoms, lasting for  $\leq$  5 days in duration.
- Isolated (i.e. no other abnormalities) Grade 3 elevation of amylase without associated clinical symptoms, lasting  $\leq$  5 days
- Grade 3 hypocalcemia, hypokalemia, hypomagnesemia, hyponatremia, or hypophosphatemia that responds to medical intervention.
- Grade 3 hypercholesterolemia.
- Grade 3 hypertriglyceridemia
- Grade 2 Alopecia
- Grade 3 Constipation
- Grade 3 Fatigue

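### The protocol gives two incompatible rules for prophylactic G-CSF in cycle 1, so cycle 1 neutropenia and the dose holds tied to it depend on which section a clinician follows

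*Combined protocol and SAP*

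**What the plan says.** Four places in the protocol speak to growth factors.

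- Section 5.1.7, general paragraph: "Post cycle 1, colony stimulating growth factors (e.g., filgrastim, peg-filgrastim, and sargramostim) may be used in patients who experience hematological toxicity".
- Section 5.1.7, Neutropenia bullet: "Prophylactic use of colony-stimulating factors including G-CSF, pegylated G-CSF or GM-CSF should not be utilized during the first cycle of therapy". It continues: "These factors may be utilized if clinically indicated in subsequent cycles".
- Section 5.3, under the heading Prophylactic Measures: "G-CSF may be given at each cycle". The only limit given there is a minimum interval for the pegylated product.
- Section 5.1.6, in the Phase 2 de-escalation text: "Specifically, for hematologic toxicities, patients may receive GCSF for neutropenia". No cycle is named.

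Section 5.2 sets the neutropenia DLT: "Hematologic dose-limiting toxicity will be defined as either Grade 4 neutropenia that does not resolve to" Grade 2 or less within 7 days. It is assessed mainly in cycle 1 and does not mention growth factors. Section 2.4.2 reports Phase I as complete, with two DLTs in the cohort declared the maximum administered dose, "which resulted in 1 Grade 4 thrombocytopenia and 1 Grade 4 neutropenia".

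**The concern.** The Neutropenia bullet in 5.1.7 and the sentence in 5.3 cannot both be followed for a cycle 1 patient who is being considered for prophylaxis. Neither refers to the other, and nothing says which governs.

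Growth-factor support acts on the neutrophil count; section 7.2.1.1 itself lists G-CSF among the measures used to manage neutropenia. Several rules use that count. Section 5.1.3 requires a minimum ANC before each treatment after cycle 1 day 1. Table 8 in section 6.3.1 holds romidepsin for Grade 3 or 4 neutropenia and reduces it permanently for febrile Grade 4 or recurrent neutropenia. Section 5.1.6 links doses missed for ANC to dose reduction. If support in cycle 1 differs by clinician, the neutropenia recorded and the doses delivered will differ for reasons unrelated to the regimen.

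This matters most for safety reporting. The Study Design text in the synopsis says safety is evaluated throughout the study. Safety and tolerability is a primary objective of the exploratory cohort in section 1.7, although the synopsis lists it as secondary.

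**Working it through.** The plan states no figure on this point, so there is none to reproduce. The check compares the texts and then gives two short calculations of scale.

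**1. The texts side by side**

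| Text | Cycle 1, prophylaxis | Cycle 1, treatment of neutropenia | Later cycles |
|---|---|---|---|
| 5.1.7, general paragraph | Use placed after cycle 1 | Use placed after cycle 1 | Allowed for patients with hematological toxicity |
| 5.1.7, Neutropenia bullet | Should not be used | Not stated | Allowed if indicated |
| 5.3, Prophylactic Measures | Allowed | Not stated separately | Allowed |
| 5.1.6, Phase 2 text | Not stated | Allowed, no cycle limit | Allowed |

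The first column holds the direct conflict, between the Neutropenia bullet and 5.3. The 5.3 sentence cannot be read as covering treatment only, because it stands under a prophylaxis heading beside tumor-lysis and anti-emetic prophylaxis. The second column holds a lesser tension: 5.1.6 concerns treatment, so it does not contradict the Neutropenia bullet and sits awkwardly only with "Post cycle 1, colony stimulating growth factors" in the general paragraph.

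**2. Scale in the cohorts still to be summarised**

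Section 13.2 gives 24 patients for Phase II and 10 for the exploratory cohort. One patient whose cycle 1 neutropenia is classified differently because of support moves the crude rate by 1/24 = 4.2 percentage points in Phase II and by 1/10 = 10 points in the exploratory cohort. The documents give no basis for estimating how many patients this would be.

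**3. How sensitive a cycle 1 duration criterion is to support (illustration only)**

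None of these inputs is in the documents:

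- o = probability of any other DLT, 10% or 20%
- g = probability of prolonged Grade 4 neutropenia without G-CSF, 10% to 30%
- e = share of those neutropenia events that G-CSF prevents: 0, 50% or 100%

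DLT probability: p = 1 − (1 − o)(1 − g(1 − e)).

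Under the escalation rule in Table 3, the chance of escalating is (1 − p)³ + 3p(1 − p)² × (1 − p)³.

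With o = 10% and g = 20%:

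- e = 0: p = 1 − 0.9 × 0.8 = 0.28; chance = 0.373 + 0.435 × 0.373 = 0.54
- e = 50%: p = 1 − 0.9 × 0.9 = 0.19; chance = 0.531 + 0.374 × 0.531 = 0.73
- e = 100%: p = 0.10; chance = 0.729 + 0.243 × 0.729 = 0.91

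Over the whole assumed range the chance of escalating is 0.25–0.73 with no events prevented, 0.45–0.82 with half prevented and 0.71–0.91 with all prevented. A DLT finding on this criterion can therefore be read properly only if one knows whether support was given. The calculation says nothing about what happened in Phase I.

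**The case against.** The strongest reply is that the conflict is a wording fault with little consequence. Phase I is finished and the Phase II dose is fixed. The Phase II decision rule uses response rate, which does not involve neutropenia. The exploratory cohort is descriptive. Section 5.3 already requires medications and supportive therapies during the study to be recorded in the CRF. All of this stands, and it limits the point to clarity and reporting.

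A reader might go further and infer that the MTD is wrong, or that removing the single neutropenia DLT would have let escalation proceed. The documents do not support this:

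- They report no cycle 1 G-CSF use in Phase I, and the Grade 4 neutropenia in cohort 7 was counted as a DLT, so it was not masked.
- Cohort 7's regimen matches Level 6, the highest level in Table 2, so there was no further level to proceed to. The cohort's size is not given, so the applicable row of Table 3 is unknown.
- Section 2.4.2 describes 21-day cycles and cohort numbers absent from the current Table 2, so it cannot be assumed that the present 5.3 sentence governed Phase I.

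Three other inferences also fail. Phase I is described as single institution, so variation between sites is not shown; it would be between clinicians or patients. The 19.2% Grade 3/4 febrile neutropenia pools 26 patients over all dose levels without restriction to cycle 1, so it does not predict how often G-CSF would be used at the Phase II dose. No comparison of cytopenia rates between phases or cohorts is planned, so none is invalidated. Finally, 5.1.7 says should not, which is softer than a prohibition.

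None of this removes the conflict in the current text.

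**Conclusion.** The contradiction is certain. For cycle 1 prophylaxis, 5.1.7 and 5.3 give opposite guidance with no order of precedence, and 5.1.6 adds a smaller ambiguity about treatment. The forward effect is on cycle 1 neutropenia, the holds and reductions driven by ANC, and the safety summaries for up to 24 + 10 = 34 patients. Its size is not estimable from the documents beyond the per-patient shifts shown above, and it rests on G-CSF altering the depth or duration of neutropenia.

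Looking back, the MTD is not shown to be wrong. What can be said is narrower: the neutropenia DLT depends on duration in cycle 1 and carries no condition on G-CSF, so the Phase I assessments cannot be fully interpreted without knowing which growth-factor rule applied. The response-rate hypotheses, boundaries and sample size in section 13.2 are unaffected. The correction should be made, but it does not call the design into question.

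**What to change.** Reconcile sections 5.1.6, 5.1.7 (both the general paragraph and the Neutropenia bullet) and 5.3 into one cycle 1 growth-factor rule that treats prophylaxis and treatment of neutropenia separately, state it once, and have the other sections refer to it. Which rule is clinically right is for the investigators; I take no position on it.

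From the concomitant-medication data that section 5.3 already requires, list cycle 1 G-CSF use beside the cycle 1 neutropenia results for Phase II and the exploratory cohort, and beside each Phase I neutropenia DLT assessment. A patient listing is enough; formal subgroup rates in 24 and 10 patients would be too sparse to help.

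The cost is an amendment to the wording, a check that the CRF holds G-CSF start and stop dates, and one additional safety listing. No sample size or analysis of the primary endpoint changes.

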### **5.4 Duration of Therapy**

Treatment may continue until one of the following criteria applies:

- Disease progression
- Unacceptable adverse event(s), DLTs
- Withdrawal of consent
- General or specific changes in the patient's condition render the patient unacceptable for further treatment in the judgment of the investigator
- An event that in the judgment of the treating physician warrant's discontinuation of therapy
- There is no pre-specified number of cycles allowed

## **5.5 Duration of Follow Up**

Patients will have an end of study visit 4 weeks +/- 5 days after their last dose of drug to evaluate safety. Patients will be further followed every three months after the 4-week safety evaluation for one year, or until they begin a new treatment for their disease, for evaluation of delayed toxicity. Patients removed from study for unacceptable adverse events will be followed until resolution or stabilization of the adverse event.

For patients who have stable disease or better after 6 cycles of therapy, tumor assessment will be performed by medical history, physical, CBC with differential and chemistries every 3 months until progression of disease occurs. CT (PET/CT optional) will not be routinely used to monitor complete responses after 6 months, but rather, will be used when indicated, due to concern for disease progression.

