**Secondary Objectives**

- Estimate the DOR and PFS of the combination in patients with T-cell lymphoma.
- Estimate the overall survival of patients with T-cell lymphoma on study.
- Identify potential pre-treatment biomarkers of response based on GEP and/or methylation array to clinical outcome.

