#### Tests

Safety evaluations on Day 1

Laboratory Evaluations Days 1, and each day of romidepsin

CT scans at the end of cycles 2 and 6. Then CT scans q3-6 months, until disease progression or initiation of new therapy.  
(PET/CT is optional)

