### **1.5 Phase II Secondary Objectives**

- Estimate the DOR and PFS of the combination in patients with T-Cell Lymphoma.
- Estimate the overall survival of patients with T-Cell Lymphoma on study.
- Identify potential pre-treatment biomarkers of response based on GEP and/or methylation array) to clinical outcome.

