## **5.6 Criteria for Removal from Study**

Patients will be removed from treatment when any of the criteria listed in Section 5.4 applies. The reason for study removal and the date the patient was removed must be documented in the Case Report Form.

Subjects/patients may withdraw at any time or be dropped from the study at the discretion of the investigator should any untoward effects occur. In addition, a subject/patient may be withdrawn by the investigator if he/she violates the study plan or for administrative and/or other safety reasons. The investigator or study coordinator will notify the appropriate parties within 2 business days when a subject has been discontinued/ withdrawn due to an adverse event (Section 7). When a subject discontinues/withdraws prior to study completion, all applicable activities scheduled for the final study visit should be performed at the time of discontinuation. Any adverse events present at the time of discontinuation/withdrawal will be followed until resolution.

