## 10. STUDY CALENDAR

Baseline evaluations are to be conducted as indicated in the table below, prior to start of protocol therapy. Scans must be done  $\leq$ 4 weeks prior to the start of therapy. In the event that the patient's condition is deteriorating, laboratory evaluations should be repeated within 48 hours prior to initiation of the next

cycle of therapy.

Cycle	Screening	1				2- onward				End of treatment	End of Study (4 weeks after last dose)	Follow-up j
		Day 1	Day 8	Day 15	Day 22	Day 1	Day 8	Day 15	Day 22			
Eligibility & Safety Monitoring												
Informed Consent	X c											
Demographics	X c											
Medical History	X c											
Concurrent Medications	X f	X g	X	X	X	X	X	X	X	X	X	X
Physical exam	X f	X g	X	X	X	X				X	X	X
Vital Signs, weight	X f	X	X	X	X	X				X	X	X
Performance Status	X f	X	X	X	X	X				X	X	X
CBC w/ differential	X f	X g	X	X	X	X	X	X	X	X	X	X
Chemistries a, i	X f	X g				X				X	X	X
EKG	X c		X				X			X	X	
Toxicity Assessment			X	X	X	X				X	X	X
Serum β-hCG	X f											
Urinalysis	X c	X g										
Creatinine clearance	X											
Drug Dispensation												
Oral 5-azacitidine		X				X						
Romidepsin			X	X	X		X	X	X			
Efficacy Measurements												
CT (PET/CT optional)	X c						X b					
Brain MRI	X c, l											
Bone Marrow Biopsy k	X									X c		
Lymph Node Assessment	X c											
PK/Biomarkers												
Lymph Node Biopsy, FNA, or Bone Marrow Biopsy (Optional)	X c		X l									
PK		X d	X d			X						
Correlative Blood Sample		X h										

a) Chemistries include: Chem \*, Mg+, K+, Creatinine, Hepatic Function Panel (LFTs, bilirubin), and LDH. On romidepsin days of cycles 2 and onward, full chemistries may be drawn, but only K+ and Mg+ are required.  
b) CT to occur after cycle 2 and 6, Then CT q3-6 months, until disease progression or initiation of new therapy at the discretion of the Investigator. (PET/CT is optional)  
c) Bone Marrow biopsy will be required after cycle 2 for patients with bone marrow involvement at baseline who have a complete response by imaging and physical exam  

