d) PK for Oral 5-azacitidine /Romidepsin: See figure 1 for details.  
e) To be done within 4 weeks of treatment start date  
f) To be done within 1 week of treatment start date  
g) Not necessary if conducted within 72 hours of screening assessment  
h) PD for Oral 5-azacitidine /Romidepsin: See figure 1 for details.  
i) Sodium, potassium, chloride, calcium, and glucose are part of the electrolyte assessment at every time point. Magnesium and phosphorous will be added to the electrolyte panel at Screening, and repeated before administration of romidepsin.  
j) Follow-up visits will be every 3 months for 1 year, or until the patient begins a new treatment for their disease for any patient that did not progressed on study.  
k) Based on clinical assessment  
l) For CNS disease only. Follow up MRI to be done at the discretion of the treating investigator.

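### Overall survival is a Phase II secondary objective, but scheduled follow-up stops at progression or new treatment and survival status is not collected afterwards

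*Combined protocol and SAP*

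**What the plan says.** The synopsis and section 1.5 both list OS among the Phase II secondary objectives: "Estimate the overall survival of patients with T-Cell Lymphoma on study". The same list includes "Estimate the DOR and PFS of the combination in patients with T-Cell Lymphoma".

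Follow-up is described in these places:

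- **Section 5.5.** After a safety visit 4 weeks after the last dose, patients are "followed every three months after the 4-week safety evaluation for one year, or until they begin a new treatment for their disease", to look for delayed toxicity. No patient group is excluded. A second paragraph keeps patients with stable disease or better after 6 cycles under 3-monthly tumour assessment until progression.
- **Section 10, footnote j.** The interval, the one-year limit and the new-treatment stop are the same, but the visits run "until the patient begins a new treatment for their disease for any patient that did not progressed on study".
- **Section 10, column headings.** The last column before follow-up is headed "End of Study (4 weeks after last dose"). The calendar has no survival-status row.
- **Phase II schema, tests in later cycles.** CT scans continue "until disease progression or initiation of new therapy". Calendar footnote b says the same, at the investigator's discretion.
- **Section 5.6.** "Any adverse events present at the time of discontinuation/withdrawal will be followed until resolution". Section 5.5 also accepts stabilization as an end point for patients removed for unacceptable events.
- **Sections 7.4.1 and 7.6.** Deaths 'on study' need expedited reports, and new adverse events are captured for 30 days after completion or withdrawal. The documents do not define 'on study'.

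The Phase II part of section 13.3 covers baseline summaries and the response rate with an exact 95% confidence interval.

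**The concern.** An OS estimate needs each patient's survival status up to death or a common cut-off, whatever happens to the disease in between. Here every scheduled contact serves toxicity or tumour assessment, and each has a stop rule linked to progression, new treatment, resolution of an event or a short window.

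Progression ends treatment under section 5.4. If contact then ends with it or soon after, patients leave the risk set just as their risk of death has probably risen. Kaplan-Meier assumes that censored patients have the same prospects as those still followed, and that would not hold. In a single-arm study there is no control arm in which a similar bias might offset this one.

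The conflict between section 5.5 and footnote j adds to the problem. A progressor who has not started new treatment is seen for up to a year under one passage and not after the 4-week visit under the other.

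**Working it through.** **What is unaffected.** The plan's only Phase II sample-size figure is the two-stage response design in section 13.2: stop at 2 or fewer responses in 9; not effective at 9 or fewer in 24; rates 25% versus 50%. Exact binomial calculation gives an early-stopping probability of 0.601 at 25%, an expected size of 9 + (1 − 0.601) × 15 = 15.0, power 0.805 and alpha 0.0485. These agree with the plan (0.60, 15, 80%, 0.049) apart from rounding of alpha. None uses OS.

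**When contact ends for a progressor.**

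| Reading | Last contact |
|---|---|
| Footnote j | 4-week visit, about 1 month after the last dose |
| Footnote j plus 30-day event capture (7.6), if completion means the 4-week visit | 4 weeks + 30 days, about 2 months |
| Section 5.5, new treatment started | start of new treatment |
| Section 5.5, no new treatment | 4 weeks + 1 year, about 13 months |

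No reading extends past new treatment, and none asks for survival status as such.

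**Illustration.** The documents give no PFS or OS inputs, so all of these are assumptions: median PFS 3, 4 or 6 months; median post-progression survival 4, 6 or 9 months; 10% or 20% of first events are deaths; exponential times; last dose at progression. That makes 18 scenarios.

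Write a = ln 2 / median PFS, b = ln 2 / median post-progression survival, and f for the share of first events that are deaths. True 12-month OS is

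f·e^(−12a) + (1 − f)·[a·e^(−12b) − b·e^(−12a)] / (a − b).

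For PFS 4, post-progression 6 and f = 0.10: a = 0.1733, b = 0.1155, e^(−12a) = 0.125, e^(−12b) = 0.25. So OS = 0.0125 + 0.9 × (0.04332 − 0.01444)/0.05776 = 0.0125 + 0.45 = 0.46. Across the grid it is 26% to 65%, or about 9 to 18 deaths in 24 patients by month 12.

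Error is the Kaplan-Meier value at 12 months minus true OS, simulated with 400,000 patients per scenario. Capture is the share of deaths by month 12 that are observed. The last column is the simulated standard deviation of the estimate with 24 patients in the worked example.

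| Progressor last seen | Error, 18 scenarios (points) | Deaths captured | Error, example | SD, N = 24 |
|---|---|---|---|---|
| 1 month after progression | +8 to +28 | 31%–49% | +23 | 15–16 |
| 2 months | +6 to +18 | 44%–59% | +16 | 15 |
| 3 months, all start new treatment | +4 to +12 | 54%–69% | +11 | 14 |
| 3 months, 25% start none (13 months) | +2 to +8 | 65%–77% | +6 | 13 |
| 3 months, 50% start none (13 months) | +1 to +5 | 77%–85% | +4 | 11–12 |

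**Direction.** In this model the death hazard is f·a before progression and b after it. The estimate is too high when b > f·a, that is, when median post-progression survival is below median PFS divided by f. In the example 4/0.10 = 40, far above 6. On the main grid the smallest ratio is 3/0.20 = 15, above 9, so every error is positive. On a wider grid (PFS 2 to 9, post-progression 3 to 12, f 5% to 30%; 100 scenarios) the condition fails in 4: PFS 2, f 0.30 with post-progression 9 or 12; PFS 2, f 0.20 with 12; PFS 3, f 0.30 with 12. The 1-month error there spans −10 to +33.

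**The case against.** The best defence is that the bias is inferred from silence. The plan states no OS censoring date, and nothing stops staff at this single institution from checking survival in charts or records. OS is secondary and descriptive, and no decision rule uses it. All of this is true. It limits the size and consequence of the point but does not supply the data: nothing requires survival to be checked, so ascertainment could differ from patient to patient.

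Several stronger readings are tempting, and the documents do not support them.

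- A reader might infer that OS will be overstated by up to 28 points. That figure needs the strictest reading of footnote j and assumed inputs. Adding the 30-day event window of section 7.6 already lowers the upper end to about 18.
- A reader might set the errors against a standard error of √(0.46 × 0.54/24) = 10 points. That formula assumes complete follow-up. Under the censoring at issue the spread in the worked example is roughly 11 to 16 points, so the 3-month error of +11 is within one standard error, and the 1-month error of +23 is about 1.5.
- A reader might infer that no post-progression death is seen. Section 5.5, read literally, keeps untreated progressors under visits, and safety reporting would catch some deaths.
- A reader might treat the lack of a time origin, estimator and censoring rule for OS, PFS and DOR in section 13.3 as a defect of equal weight. It is missing detail that an analyst would fill conventionally, and it does not carry this point.

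It could also be said that 'on study' limits OS to survival during participation. The term is undefined, so the text does not settle this.

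**Conclusion.** The gap and the conflict are plain from the text: OS is an objective, its data are not collected after progression or new treatment, and section 5.5 and footnote j disagree on whether progressors are followed. Followed as written, the plan cannot deliver an unbiased OS estimate.

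The error is probably upward, because death is usually more likely after progression than before it, but this is not certain. Its size cannot be fixed from the documents. The range of about +1 to +28 points at 12 months rests entirely on the assumed PFS, post-progression survival, share of deaths as first event and lag. Under several readings the error is smaller than the sampling error of a 24-patient study.

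This should be corrected, but it does not threaten the trial's main conclusion. One limit: the consent pages and a few other passages are absent from the public copy and could not be checked.

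**What to change.** Reconcile section 5.5 with footnote j, so that both say the same about patients who progressed. Then choose one of two routes.

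1. **Collect survival.** Add a calendar row and a sentence such as: *Survival status is obtained about every 3 months by telephone, chart or record check for every treated Phase II patient, regardless of progression or new therapy, until death or a stated cut-off date; OS is censored at the date last known alive.*
2. **No new contacts.** Drop OS as an objective, or define 'on study' and label the estimate as survival during that period only.

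Route 1 costs a short amendment and brief contacts or record checks for up to 24 patients. Consent must cover them; whether it does now cannot be judged from this copy. Route 2 costs only text. Neither changes the sample size or the response analysis.

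A useful accompaniment is to write OS, PFS and DOR into section 13.3: time origin, event, censoring date, handling of new therapy before progression, and Kaplan-Meier with a 95% confidence interval. For PFS and DOR, also align the imaging schedule, since section 5.5 drops routine CT for complete responses after 6 months while calendar footnote b keeps it every 3 to 6 months.
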